5. TRIAL DESIGN

The overall trial design, depicted in the flowchart below, is a parallel group, open label study randomising to RFW or FAW in permuted blocks in adults aged 60 years or over who are undergoing hemiarthroplasty following hip fracture. The trial has been designed with input from cross-specialty hospital consultants, patient representatives, a statistician and a clinical trials unit. This pilot study will recruit for a minimum of one year at each site, allowing for refinements to design, site selection and, if necessary, the data management strategy in preparation for a large multi-centre trial.

Participants will be expected to remain in the trial for approximately three months. They will not need to attend any research specific clinics or undergo any study specific clinical investigations. The primary endpoint is numbers recruited and observed event rate for definitive deep surgical site infection (SSI) within 90 days as defined by the Centre for Disease Control (CDC). All potential primary endpoints will be confirmed by a blinded endpoint committee. The secondary endpoints include serious adverse events including death, superficial SSI, IPH, length of hospital stay, patient reported outcome measures (EQ-5D-5L) and resource utilisation. Data for all assessments will be captured either from routine clinical care records or by telephone contact with participants or their GP practice at baseline, 30 (+/- 7) days and 90 (+/- 14) days. Patients will be flagged and mortality checks performed at each time point before the local study team makes contact for follow-up. Where a potential deep SSI is identified, a summary of the clinical care record, redacted for all personal identifiable information and any indication of randomisation arm, will be forwarded to the independent blinded endpoint committee.

CONFIDENTIAL Page 11 of 34

Endpoint Committee

The endpoint committee, which will remain blind to allocation, will comprise clinicians with expertise in the diagnosis and management of bone and joint infection. The committee will have a chair and two other members. If any endpoint committee member stands down during the course of the trial, they will be replaced by someone with similar background and qualifications.

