Any post-randomisation re-admission, clinic attendance or return to theatre with signs and symptoms at the site of surgery (i.e. possible deep surgical site infections) will be considered a potential primary endpoint. A summary of the relevant medical record, redacted for personal identifiers and information relating to randomisation, will be forwarded to the blinded endpoint committee who will determine if an endpoint has been met. Determination of an endpoint will be by consensus following discussion or by a majority vote called by the chair if consensus cannot be reached.

Secondary endpoints, including SAEs and data for resource utilisation, will be determined directly by the local investigators.

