7.4. Randomisation and limitation of bias

Prior to surgery, participants will be randomised 1:1 in randomly permuted blocks through an established software package to either Forced Air Warming or direct contact Resistive Fabric Warming. No stratification factors will be employed. In case of software failure, randomisation envelopes will be prepared in advance under the supervision of a qualified statistician and held by the local study team for immediate use in the emergency setting.

This will be an open label trial. Although participants will not be directly informed of their randomised allocation, they may become aware of this either immediately before or upon recovery from anaesthesia. Similarly, it is not possible to blind the direct medical care team or the local study team as to which warming technology is utilised during surgery. Any consequent risk of bias will be limited by the use of a blinded end point committee for the assessment of relevant potential endpoints. For all potential deep SSIs, the end point committee will be provided with a summary of the participant's medical records relevant to the clinical episode, (including presentation, operative findings, laboratory results, radiology reports and treatment) redacted for personal identifiers and any information relating to their randomisation or intraoperative thermoregulation. At the time of randomisation, the participant's initials, NHS number and a computer-generated study number will be recorded on an enrolment log. Justification for use of NHS numbers comes from previous multicentre studies in which the randomisation software requires all

participants to have a primary identifier of the same alphanumeric structure and with no opportunity for duplicates.

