7.6. Subsequent Assessments

The participant will be contacted for follow-up at the following time points after surgery:

- 1) 30 (+/- 7) days
- 2) 90 (+/- 14) days

Follow-up assessments will be undertaken by a member of the local study team through a) medical records and b) direct contact, usually by telephone, with the participant or their consultee. The participant will not be asked to attend any research specific clinic visits and they will not be visited at home by the study team. If it is not possible to make contact with the participant, the local study team will gather follow-up data from the patient's GP and from routinely collected surveillance data. At each time point, we will ask questions about the participant's wellbeing, surgical scar and any treatment or concerns around possible infection at the operative site. Where necessary, further clinical review will be requested.

The study will use the participant follow-up telephone questionnaire in Appendix A as a research tool when gathering patient reported outcome measures for quality of life (PROMS) and any relevant concerns they have. Instructions to the participant will be dictated from the EQ-5D-5L telephone questionnaire in Appendix B. If a patient lacks capacity, the EQ-5D-5L Proxy version 1 will be used (Appendix C).

Deep SSI will be defined by the following criteria:

- a. Infection arising within 90 days of the index surgery (where day 1 is the procedure date) AND
- b. Involves deep tissues related to the incision (e.g. fascial and muscle layers, joint space or periprosthetic region)

AND

- c. At least one of the following
 - i. Purulent drainage from the deep incision or periprosthetic drain.
 - ii. A deep incision that spontaneously dehisces, or is deliberately opened or aspirated or biopsied by a surgeon, physician or other designee and an organism is identified by a culture or non-culture based microbiologic testing method which is performed for purposes of clinical diagnosis or treatment (e.g., not Active Surveillance Culture/Testing) or culture or non-culture based microbiologic testing method is not performed
 - An abscess or other evidence of infection involving the deep incision or periprosthetic region that is detected on gross anatomical, histopathological exam or imaging test

Superficial SSI will be defined by the following criteria:

- a. Infection arising within 30 days of the index surgery (where day 1 is the procedure date) AND

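### The blinded endpoint committee decides deep SSI on a redacted summary whose preparer is neither named nor required to be blind, with no stated route to the underlying records

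*Protocol*

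**What the plan says.** Three places in the Protocol set what the committee sees, and each makes it a summary.

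- Section 5, main text: for a potential deep SSI the committee receives "a summary of the clinical care record, redacted for all personal identifiable information and any indication of randomisation arm".
- Section 5, Endpoint Committee: "A summary of the relevant medical record, redacted for personal identifiers and information relating to randomisation, will be forwarded to the blinded endpoint committee". The committee then rules by consensus or, failing that, by majority vote.
- Section 7.4: the summary covers the clinical episode, "including presentation, operative findings, laboratory results, radiology reports and treatment", and is "redacted for personal identifiers and any information relating to their randomisation or intraoperative thermoregulation".

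Section 7.4 also explains why the committee exists. It states that "it is not possible to blind the direct medical care team or the local study team as to which warming technology is utilised during surgery", and then: "Any consequent risk of bias will be limited by the use of a blinded end point committee".

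On who handles the case material, section 7.6 says "Follow-up assessments will be undertaken by a member of the local study team", using medical records and direct contact. Section 12.2 gives completion of the electronic CRF to the same team. No section names the person who writes or redacts the summary. The only source document offered for clarification (section 7.6) is the CDC criteria, not the patient's notes.

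**The concern.** A blinded committee protects against open-label bias only as far as its evidence is independent of allocation. Redaction takes out the arm label. It does not undo a choice, made by someone who knew the arm, about which findings to include or how to describe them. Referring every suspected case would not help, because the gap lies in what the committee reads about each case.

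Several deep SSI criteria in section 7.6 need judgement: whether drainage was purulent, whether deep tissue was involved, and what counts as other evidence of infection. For such items, the completeness and phrasing of a summary could decide the ruling.

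The observed deep SSI rate is part of the pilot's primary endpoint (sections 1 and 5). Section 3 says pilot data will be carried into the final analysis of the full trial, so the committee's pilot rulings would stand there too.

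**Working it through.** **1. What is fixed and what is open.**

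- Form of the evidence: fixed as a summary in all three places.
- Content: fixed in section 7.4 under five headings. Laboratory results and radiology reports are mostly existing reports. Presentation and operative findings are narrative. The headings do not require verbatim text or every sample.
- Preparer: not stated. Sections 5 and 7.4 use the passive voice.
- Blindness of the preparer: not required. The only group described as gathering case data (sections 7.6 and 12.2) is one that section 7.4 says cannot be blinded.
- Committee access to the records: none stated.

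**2. Redaction scope.** Section 7.4 removes randomisation and intraoperative thermoregulation. The main text of section 5 removes any indication of arm, which largely covers the same ground. The Endpoint Committee text mentions only randomisation and is the narrowest. This is uneven wording, not a conflict.

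**3. The plan's own figure.** Inputs from section 3: 2.5% against 1.5%, 90% power, 5% level. Section 7.4 gives 1:1 allocation. A two-sided test is assumed, since sidedness is not stated.

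n = [1.960·√(2·p̄·(1−p̄)) + 1.282·√(p1(1−p1) + p2(1−p2))]² / d², with p̄ = 0.02 and d = 0.01

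n = (0.3881 + 0.2536)² / 0.0001 ≈ 4117 per arm

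With continuity correction: n′ = (n/4)·[1 + √(1 + 4/(n·d))]² ≈ 4315 per arm, or 8630 in total. The stated figure is reproduced and this point does not affect it.

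**4. Illustration of differential confirmation.** The confirmation percentages are assumptions; the documents give none. Take 4315 per arm and a true rate of 2.5% in both arms, with 100% of true cases confirmed in one arm and a share s in the other.

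p1 = 0.025, p2 = 0.025·s, d = p1 − p2

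se0 = √(2·p̄(1−p̄)/4315), se1 = √([p1(1−p1) + p2(1−p2)]/4315)

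P(reject) = Φ((d − 1.96·se0)/se1) + Φ((−d − 1.96·se0)/se1)

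For s = 0.90: d = 0.0025 and se0 ≈ se1 ≈ 0.00328, so P = Φ(−1.20) + Φ(−2.72) ≈ 0.116 + 0.003 = 0.119.

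| s | Confirmed events per arm | Type I error |
|---|---|---|
| 1.00 | 107.9 v 107.9 | 5.0% |
| 0.95 | 107.9 v 102.5 | 6.6% |
| 0.90 | 107.9 v 97.1 | 11.9% |

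Simulating the Wald test of the log odds ratio (400,000 replicates) gives 6.5% and 11.7% for the last two rows.

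**5. Differential against equal loss.** With true rates of 2.5% and 1.5%, power at 4315 per arm is 91.3% without continuity correction. Confirming 90% in the higher-rate arm only gives 72.9%. Confirming 90% in both arms gives 88.2%. Loss that differs by arm does most of the harm.

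**6. Scale of the pilot.** Three centres at a minimum of 100 each (section 7.1) make 300 participants. At 2.5% that is 300 × 0.025 = 7.5 cases, against about 2 × 107.9 = 216 in the null scenario of step 4.

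**The case against.** A reader might infer that the committee's rulings do rest on an unblinded selection of facts, because the records are at site and the site teams know the arm. The documents do not go that far. They never name the preparer, and an endpoint committee charter, which is not among them, could assign a blinded one. What can be said is that the protocol does not exclude an unblinded preparer.

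Section 7.4's five headings already meet part of the concern, since they narrow the room for selection. They leave the narrative items and the completeness of results open.

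Source pages would not cure everything. Whether fluid is recorded as pus is first written by treating clinicians, who are also unblinded. Verbatim copies pass that wording on. They remove only what summarising adds.

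The illustration needs loss in one direction across sites. Section 14.7 describes one site using FAW only, one using RFW only and one using both, with investigators in equipoise, so local leanings need not align. Nor may the 12% figure be read onto the pilot: section 10.1 plans no formal efficacy analysis unless recruitment passes 1000, and section 10.3 leaves the full trial's analysis open to revision after the pilot.

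These objections limit the size and certainty of the point. None supplies a named blind preparer or a route to the records.

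**Conclusion.** The point holds as a weakness in the stated method. The one safeguard the protocol names against open-label bias works from a summary, with no stated preparer, no blinding requirement for that person and no access to the records behind it. Selection or phrasing by arm is possible; the documents give no evidence that it happens. The redaction wording should be made uniform, but it is not a contradiction.

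The effect is unknown. At the definitive trial's size, and only under the assumed differentials of 5 and 10 percentage points in confirmation, type I error would be about 6.5% and about 12%. With 7 or 8 expected cases in a pilot of 300, no such figure applies to the pilot. The reason to act early is that the remedy is cheap and the pilot's rulings are meant to carry forward.

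**What to change.** In both parts of section 5 and in section 7.4, replace the summary with redacted verbatim copies of the documents under the section 7.4 headings:

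- presentation or clinic notes
- the operation note of any return to theatre
- all microbiology and histology results
- imaging reports
- the treatment record

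Use the section 7.4 redaction scope (randomisation and intraoperative thermoregulation) in all three places. State which role compiles and redacts the pack, and let the committee request further redacted records.

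The cost is wording in three places, plus copying and redaction. If two to three cases are referred per confirmed case (an assumption), 7.5 confirmed cases per 300 participants mean about 15 to 23 packs, or 5% to 7.5% of participants. The referral trigger in section 5 is broad, so the number may be higher. Packs will be longer, and there is a small added risk that redaction misses a clue to allocation. That risk is limited because the listed documents concern the later infection episode rather than the index operation.

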- b. Involves only skin or subcutaneous tissue related to the incision AND
- c. At least one of the following
 - i. Purulent drainage from the superficial incision
 - ii. Organisms identified from an aseptically-obtained specimen from the superficial incision or subcutaneous tissue by a culture or non-culture based microbiologic testing method which is performed for purposes of clinical diagnosis or treatment (e.g., not Active Surveillance Culture/Testing (ASC/AST).
 - Superficial incision that is deliberately opened by a surgeon, physician or other designee and culture or non-culture based testing is not performed AND
 the patient has at least one of the following signs or symptoms: pain or tenderness, localized swelling, erythema, heat
 - iv. Diagnosis of a superficial incisional SSI by a surgeon or physician.

The above definitions are adapted from the CDC surgical site infection criteria published January 2016. If required for clarification or consensus, investigators and the EPC will be referred back to the source document.

Serious adverse events (SAEs), including death (i.e. all-cause mortality), will be recorded.

Discontinuation/Withdrawal of Participants from Study

Once a participant has been randomised, they will ordinarily be included in the intention to treat (ITT) analysis. However, the Principal Investigator at each site will withdraw any randomised participant from the study if they do not subsequently undergo surgery. Each participant or their consultee has the right to withdraw from the study at any time with no obligation to give a reason for withdrawing. The participant will be asked whether or not they will allow passive follow up using routinely available NHS data. All data collected up until the point of withdrawal of consent will be included in the final analysis unless requested otherwise by the participant.

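### Superficial SSI, a judgement-based secondary endpoint, is determined by unblinded local investigators, and the blinded committee is not asked to rule on it

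*Protocol*

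**What the plan says.** Section 5 lists the endpoint: "The secondary endpoints include serious adverse events including death, superficial SSI, IPH, length of hospital stay". Under its Endpoint Committee heading, the same section assigns the decision: "Secondary endpoints, including SAEs and data for resource utilisation, will be determined directly by the local investigators".

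Section 7.4 says of the open-label design that "it is not possible to blind the direct medical care team or the local study team". Of participants it says: "Although participants will not be directly informed of their randomised allocation, they may become aware of this". Section 7.6 adds: "Follow-up assessments will be undertaken by a member of the local study team". That contact includes the questions about the scar and possible infection.

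Section 7.6 defines superficial SSI by three joint conditions: onset within 30 days of surgery, a depth condition ("Involves only skin or subcutaneous tissue related to the incision"), and at least one of four alternatives, c(i) to c(iv). Alternative c(iv) reads: "Diagnosis of a superficial incisional SSI by a surgeon or physician". It requires no accompanying sign, drainage or culture.

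The stated safeguard in section 7.4 is a blinded committee for the relevant potential endpoints. Sections 5 and 7.4 then describe its work as potential deep SSI, that is, the primary endpoint. Under section 5 it receives redacted summaries of any readmission, clinic attendance or return to theatre with signs and symptoms at the operative site.

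**The concern.** In a trial about infection, superficial SSI is a natural companion to deep SSI and is likely to be read as supporting or contradicting it. Unlike death or length of stay, it depends on judgement: whether a red or tender wound counts as infected, and how deep the process goes. The people making that judgement know which device was used.

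The protocol recognises the risk of bias from the open label, but its remedy stops at deep SSI. If clinicians or investigators labelled borderline wounds differently by arm, the superficial SSI estimate and its confidence interval would both move. The recorded data as described could not show this, because nothing in the protocol requires a record of which of c(i) to c(iv) each case met.

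**Working it through.** **Who decides, and on what**

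| Question | Deep SSI | Superficial SSI |
|---|---|---|
| Decided by | Blinded committee (5, 7.4) | Local investigators (5) |
| Decider knows the arm | No, dossier redacted | Yes (7.4) |
| Clinician's diagnosis alone satisfies part c | Not listed (7.6) | Yes, c(iv), given parts a and b (7.6) |
| Redacted dossier reaches the committee | Readmission, clinic attendance or return to theatre with site signs (5) | Same dossiers, where the event triggered one, but no instruction to classify it as superficial |

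A superficial infection known only through the GP or the telephone call is not named in the committee's trigger.

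**The plan's own sample size (section 3)**

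Inputs: 2.5% against 1.5%, 90% power, 5% significance, taken as two-sided, 1:1 allocation.

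- Uncorrected: n0 = [1.96 × √(2 × 0.02 × 0.98) + 1.2816 × √(0.025 × 0.975 + 0.015 × 0.985)]² / 0.01² = 4,116.8 per arm.
- Continuity-corrected: n = (n0/4) × [1 + √(1 + 4/(n0 × 0.01))]² = 4,314.5, so 4,315 per arm and 8,630 in total.

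This reproduces the stated 8,630. Nothing in this point questions it; it only supplies the size of the definitive trial.

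**Assumed superficial SSI rate**

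Section 3 gives all SSI after hip fracture repair as 2.3% (passive surveillance) to 7.3% (active surveillance), about half of it deep. Taking the other half as superficial gives 2.3%/2 = 1.15% to 7.3%/2 = 3.65%. The middle value of 2.5% used below matches the protocol's deep SSI rate.

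**Illustration: no true effect, 20% over-recording in one arm**

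Let p0 be the true rate in both arms, p1 = 1.2 × p0 the recorded rate in the affected arm, and p̄ their mean. Then:

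- SE0 = √(2p̄(1 − p̄)/n)
- SE1 = √([p1(1 − p1) + p0(1 − p0)]/n)
- P(nominally significant excess in that arm) = Φ[(p1 − p0 − 1.96 × SE0)/SE1]

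At p0 = 2.5% and n = 4,315: p1 − p0 = 0.0050 and both SEs are 0.00352, so Φ(−0.54) = 0.295.

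| Assumed rate | Spurious difference (points) | n = 4,315 per arm | n = 500 per arm | n = 150 per arm |
|---|---|---|---|---|
| 1.15% | 0.23 | 16% | 5% | 4% |
| 2.5% | 0.50 | 29% | 7% | 5% |
| 3.65% | 0.73 | 41% | 8% | 5% |

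Without bias each cell would be 2.5%. The spurious odds ratio is about 1.20 to 1.21 in every row. At 2.5% and 4,315 per arm, 10% over-recording gives 11% and 30% gives 55%.

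The 150 per arm comes from the three initial centres at the minimum of 100 each (3 × 100/2; section 7.1). The 500 per arm is the 1,000-participant threshold for a formal efficacy analysis (section 10.1). At 150 per arm only about 150 × 0.0115 = 1.7 to 150 × 0.0365 = 5.5 events per arm are expected, so the normal approximation is rough there.

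The 20% applies to all superficial events. If the bias acted only through c(iv) and, say, half of events rested on c(iv) alone, over-recording among those would have to be 20%/0.5 = 40% to give the same figures.

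**The case against.** Much of the opposing case stands.

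- **The c(iv) diagnosis is not sufficient by itself.** The 30-day and depth conditions must also hold. That is correct, although the depth condition is itself a clinical judgement.
- **The endpoint is not wholly outside the committee's view.** Superficial cases that lead to readmission, a clinic visit or a return to theatre already generate a redacted dossier. What is missing is an instruction to classify them. A reader might infer that superficial SSI has no protection at all; the documents do not support that.
- **The path of non-deep cases is not described.** A reader might infer that a case judged not deep goes back to the same investigator for the superficial decision. That is consistent with local determination of secondary endpoints, but the protocol does not say it.
- **Preference is not established.** Section 14.7 says device choice currently depends partly on team preference, but it also records equipoise at all three initial sites. One of these uses only forced air and another only resistive fabric, so any habits could pull in opposite directions and partly cancel. The illustration assumes one common direction.
- **The division of labour is disclosed.** Section 7.4 speaks of limiting bias for relevant endpoints, and section 5 openly leaves secondary endpoints to the sites. This is a design choice, not a contradiction. The definition is stated to be adapted from published CDC criteria, so c(iv) is not shown to be a drafting fault.
- **The endpoint is reported mainly by estimation.** The pilot summarises outcomes with confidence intervals where appropriate (10.1), and the provisional plan for the full trial's secondary analyses plays down testing (10.3). This lowers the severity but does not remove the point: bias moves an estimate and its interval as surely as a p-value, and section 10.3 relies on consistency of point estimates.

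That this is a pilot is only a partial answer, because section 3 carries pilot data into the final analysis of the full trial. A criterion not recorded now may be hard to recover later.

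**Conclusion.** The point holds as a gap in the protection of a secondary endpoint, of minor to moderate severity. Superficial SSI is decided by people who know the allocation, under a definition that a clinician's diagnosis can complete, and the committee offered as the safeguard is not asked about it.

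The size of any bias is unknown and the documents give no basis for one. On the assumed 20% over-recording in one arm, a superficial rate of 1.15% to 3.65% and a single direction of bias across sites, the chance of a spurious excess is about 16% to 41% in the definitive trial and about 4% to 5% in a 300-participant pilot, against 2.5% without bias. A reader might infer that the pilot's own results are at serious risk; at pilot size these figures do not support that. The deep SSI endpoint and the sample size are unaffected.

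**What to change.** 1. In section 5, ask the existing committee to classify each dossier it already receives as deep, superficial or no SSI, and use that classification for those cases.
2. Record in the CRF which of c(i) to c(iv) was met for every superficial SSI, and report a sensitivity analysis excluding cases that meet only c(iv). The analysis itself may sit in the SAP, but the data item has to be collected from the start.
3. State in section 7.4 that locally determined superficial SSI not seen by the committee remains unblinded.

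The cost is slightly more committee work per dossier, one CRF field and one extra analysis, with no new staff. Building new dossiers for every GP- or telephone-reported case would close more of the gap, but that is a workload trade-off and is not needed here. Those cases remain unblinded, and the sensitivity analysis shows how far the result depends on diagnosis-only events.
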